5.0 CLINICAL TRIAL INVESTIGATIONAL PRODUCT INFORMATION

5.1 INVESTIGATIONAL PRODUCT (IP) AND STUDY DEVICE

5.1.1 **INO-4800 AND PLACEBO**

Investigational product is defined as a pharmaceutical form of an active ingredient or placebo being tested or used as a reference in the study, whether blinded or unblinded.

INO-4800 is the active investigational product to be used in this study. The INO-4800 drug product contains 10 mg/mL of the DNA plasmid pGX9501 in 1X SSC buffer (150 mM sodium chloride and 15 mM sodium citrate). pGX9501 is a DNA plasmid expressing a synthetic consensus (SynCon[®]) sequence of the SARS-CoV-2 full length Spike glycoprotein.

Phase 2 segment:

Active Investigational Product (INO-4800): A volume of 0.4 mL will be filled into 2-mL glass vials that are fitted with rubber stoppers and sealed aluminum caps.

Placebo (placebo for INO-4800): Sterile saline sodium citrate (SSC) buffer, which contains sterile 150 mM sodium chloride and 15 mM sodium citrate in 10-mL glass vials, stoppered, and sealed with aluminum caps.

Phase 3 segment:

Active Investigational Product (INO-4800): A volume of 0.4 mL or 0.8 mL will be filled into 2-mL glass vials that are fitted with rubber stoppers and sealed aluminum caps.

Placebo (placebo for INO-4800): Sterile saline sodium citrate (SSC) buffer, which contains sterile 150 mM sodium chloride and 15 mM sodium citrate at a volume of 0.8 mL in 2-mL glass vials, stoppered, and sealed with aluminum caps.

5.1.2 **CELLECTRA® 2000**

Electroporation is a procedure used to enhance cellular DNA uptake within host cells following DNA vaccine ID delivery. This study will use the CELLECTRA[®] 2000, a portable, battery-powered medical device designed to generate a controlled, electric field that temporarily and reversibly increases cellular membrane permeability without clinically damaging the tissue. During the period of increased permeability, injected plasmid DNA can be introduced into the cells.

As mentioned above, the CELLECTRA® 2000 device is intended to enhance the uptake and expression of DNA plasmid-based biologics in order to enhance vaccine efficacy. The

INO-4800	COVID19-311
Inovio Pharmaceuticals, Inc.	Clinical Protocol

DNA plasmid is delivered separately via needle and syringe ID injection immediately prior to the electroporation. The electroporation is accomplished through a sterile, disposable needle Array attached to an Applicator delivering controlled electrical pulses as follows:

- An EP administration consists of four pulses.
- An array of three stainless steel electrode needles is used to deliver the electrical pulses into the tissue. The Array needle length that penetrates into the skin and tissue is approximately 3.2 mm. To date, we have not had any safety concerns associated with the depth of the array electrode needles. Within the Array needle depth of 3.2 mm, there are no major blood vessels (arteries, veins) or nerve structures at the authorized sites of administration overlying the deltoid or the anterolateral quadricep muscle. There are superficial capillaries and minor nerves innervating the skin, including subcutaneous tissues that may be disrupted by needle insertion, but are extremely unlikely to result in serious injury; intradermal injection followed by EP of these structures poses no significant risk to the subject except for possibly injection site reactions.
- The CELLECTRA[®] 2000 generates four 52ms ±1ms electrical current controlled DC pulses. The nominal current is set to 0.2A ±10% by modulating voltage, or capped at 200V ±5%, determined by patient tissue impedance.
- The total energy delivered by the device is determined by the combination of four device parameters: Pulse Current, Pulse Voltage, Number of Pulses, and Pulse Width. The parameters are pre-set by Inovio to be a pulse current of 0.2A, a pulse voltage of 200V, and 4 pulses at 52ms pulse width. The parameters are verified prior to shipment and cannot be changed by the user.
- In eight clinical trials administering ID injection followed by EP using the CELLECTRA® 2000, total energy delivered ranged from 0.9J to 7.8J, which have been generally safe and well-tolerated. In addition, Inovio has calculated the total maximum energy delivered ID as 8.32J for normal use conditions. Higher energy pulses ranging from 10.7J to 11.7J were evaluated in a guinea pig model which induced erythema localized to the electrode insertion site. Taken together, these nonclinical data and Inovio's clinical experience provide evidence that the total energy delivered by the CELLECTRA® 2000 device will not result in unacceptable risks when delivered to patients. Further, a published study evaluated the Visual Analog Scale (VAS) pain scores of normal use conditions (0.2A), and found ID injection followed by EP using the CELLECTRA® 2000 device to be safe and well tolerated [63].
- The specified current is constantly maintained through voltage modulation using an analog feedback loop. Measurements of voltage and current are processed for error reporting and collected for data logging.

The CELLECTRA® 2000 device is comprised of three components: (1) A battery-powered Pulse Generator, (2) an ID Applicator that is connected to the pulse generator, and (3) a three-point sterile disposable ID Array of stainless steel needles. The Pulse Generator and ID Applicator are reusable components. These components should be cleaned and disinfected prior to each subject's use according to the Cleaning and Maintenance procedure in the User Manual. The Pulse Generator and ID Applicator have been validated for up to 30 cleaning and disinfection cycles based on a maximum of 30 subjects being treated in a day. Therefore, the Pulse Generator and ID Applicator's use should be limited to 30 subjects in a day. Any potential risk of damage to the device due to cleaning

INO-4800	COVID19-311
Inovio Pharmaceuticals, Inc.	Clinical Protocol

and disinfection for more than 30 cycles has not been validated. Always inspect the device before use according to the instructions in the Maintenance section of the User Manual.

5.2 **Dosing Regimens**

Phase 2 Segment

- Active Investigational Product: One or two 1.0mg ID injection(s) of INO-4800 (~0.1mL dose volume each) followed immediately by EP administered on Day 0 and Day 28 (±3 days)
- Placebo: One or two ID injection(s) of placebo for INO-4800 (~0.1mL) followed immediately by EP administered on Day 0 and Day 28 (±3 days)

Phase 3 Segment

- Active Investigational Product: Two 1.0mg ID injections of INO-4800 (~0.1mL dose volume) followed immediately by EP administered in separate limbs on Day 0 and Day 28 (±3 days)
- Placebo: Two ID injections of placebo for INO-4800 (~0.1mL) followed immediately by EP administered in separate limbs on Day 0 and Day 28 (±3 days)

5.2.1 BLINDING

This study is blinded. The Sponsor, subjects and clinical site staff, with the exception of the site's pharmacy personnel, will be blinded. There is no difference in appearance between INO-4800 and the placebo; however, they are distinguishable based on the vial size and/or labelling on the vials. In the Phase 2 segment, the vials will be of different sizes and have unblinded labelling. In the Phase 3 segment, the vials will be the same size but will have unblinded labelling. To maintain the blind, vials will only be handled by designated unblinded personnel (site pharmacist) at the site.

Under exceptional circumstances, the PI may desire to unblind a subject's dose assignment in case of an emergency or serious medical condition when knowledge of the study product or dose is deemed by the PI to be absolutely essential for proper clinical management of the subject. Under such emergency circumstances, the Sponsor urges the PI to first contact the Medical Monitor (MM) to review options before unblinding the subject's dose assignment. In case of non-emergency, PI must contact MM to discuss the options before unblinding the subject's dose assignment.

The Phase 2 segment of the trial will be unblinded following subjects reaching the Week 30 visit. For the Phase 3 segment, it is not deemed appropriate to unblind a subject's treatment assignment for the purpose of assisting the subject in making a decision regarding receipt a different COVID-19 vaccine (emergency use or licensed vaccine). Subjects may be advised that without efficacy data, INO-4800 has not been proven to be more protective than placebo in the prevention of COVID-19 and SARS-CoV-2 infection. The Sponsor's pharmacovigilance staff may unblind a subject's dose assignment for an SAE, unanticipated adverse device effect (UADE), or adverse event of special interest (AESI) when the event is assessed as related and unexpected. If expedited regulatory reporting is required for such an event, the report may be submitted to regulatory authorities with the subject's dose assignment, in accordance with local regulations.

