- Based upon the wide availability of EUA and licensed vaccines in the US and completion of the data collection towards the Phase 3 dose selection, the Sponsor recognizes that subjects may want to know whether they received INO-4800 or placebo in order to make fully informed choices about receiving a non-study prophylactic COVID-19 vaccine (either authorized under emergency use or when licensed). Therefore, the Phase 2 segment of the study will be unblinded after all subjects have reached the Week 30 Visit timepoint.
- Clarifications have been included within the stopping rules (Section 7.8.4) to clarify that stopping rules apply to both IP and device related events.
- Clarifications have been included within the instructions for reporting of device-related complaints or deficiencies (Section 7.13) to clarify that the Sponsor will review any reported device complaints for potential hazards that could cause an SAE and determine whether the Safety Review Committee (SRC) Chair should be notified.

Protocol Version: 2.0USA

TABLE OF CONTENTS

Summar	y of Changes	4
Table of	Contents	5
Clinical F	Protocol Synopsis	10
Table 3 -	– Phase 2 Segment Schedule of Events	21
Table 4	– Phase 3 Segment Schedule of Events	23
1.0	Introduction	25
1.1	Background and Scientific Rationale	
1.2	Background Information	25
1.2.		
1.2.	2 Current Treatment and Unmet Need	27
1.3	Rationale for prophylactic vaccine development	28
1.3.	1 DNA Vaccines	28
1.3.	2 Use of Electroporation with DNA Vaccines	29
1.3.	3 Inovio's Proprietary Technology Against COVID-19	29
1.3.	4 Nonhuman Primate (NHP) Challenge Studies Following Vaccination wit	
1.3.	5 First-In-Human Phase 1 Trial of INO-4800	30
1.3.	6 Proposed Phase 2/3 Trial of INO-4800	31
1.3.	6.1 Safety and tolerability of INO-4800	32
1.3.	6.2 Nonclinical INO-4800 Data in Support of Potential Efficacy	32
1.3.	6.3 Potential Role of INO-4800 as a Booster	32
1.3.	6.4 Thermostability of INO-4800	32
1.3.	7 Dose and Regimen Rationale	33
1.3.	7.1 Binding Antibody Response	33
1.3.	7.2 Neutralizing Antibody Response	33
1.3.	7.3 ELISPOT analysis	34
1.4	Risks and Potential Benefits	34
1.4.	1 Potential Benefits	34
1.4.	2 Product Risks	34
1.4.	3 Overall Benefit/Risk Conclusion	36
2.0	Objectives and Purpose	36
2.1	Hypothesis	36
3.0	Clinical Trial Design and Endpoints	37
3.1	Primary Objectives	38
3.2	Primary Endpoints	39
3.3	Secondary Objectives	

INO-480 Inovio P	0 harmaceuticals, Inc.	COVID19-311 Clinical Protocol
3.4	Secondary Endpoints	

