6.1.2 CLINICAL TRIAL EVALUATIONS AND PROCEDURES

Once eligibility has been confirmed, the subject will be randomized to receive a treatment assignment (INO-4800 or placebo). Visit dates and windows must be calculated from Day 0, unless otherwise noted. All subjects will be followed until the Day 393 Visit. All subjects will be followed in accordance with assessments outlined below.

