8.4 ANALYTICAL POPULATIONS

Analysis populations will be:

The per-protocol (PP) population includes all subjects who receive all doses of Study Treatments and have no protocol violations. Subjects in the PP population will be grouped to treatment arms as randomized. Subjects excluded from the PP population will be identified and documented prior to unblinding of the trial database. Analyses on the PP population among those who are baseline SARS-CoV-2 seronegative will be primary for the analyses of efficacy in the Phase 3 segment of this trial.

The modified intention to treat (mITT) population includes all subjects who receive at least one dose of Study Treatment. Subjects in this population will be grouped to treatment arms as randomized. Analysis of the mITT population will be considered supportive for the corresponding PP population for the analyses of efficacy in the Phase 3 segment of this trial.

The intention to treat (ITT) population includes all subjects who are randomized. Subjects in this sample will be grouped to treatment arms as randomized. Analysis of the ITT population will be considered supportive for the corresponding PP population for the analyses of efficacy in the Phase 3 segment of this trial.

The safety analysis population includes all subjects who receive at least one dose of Study Treatment. Subjects will be analyzed according to the treatments received.

8.5 **DESCRIPTION OF STATISTICAL METHODS**

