8.5.1 PRIMARY ANALYSIS

Phase 2 Segment

Post-baseline increases from baseline in interferon-γ ELISpot response magnitudes will be compared between treatment groups using differences in medians and associated non-parametric 95% CIs.

INO-4800	COVID19-311
Inovio Pharmaceuticals, Inc.	Clinical Protocol

Post-baseline increases from baseline in neutralizing antibody response titers will be compared between treatment groups using ratios of geometric mean fold-rises and associated t-distribution based 95% CIs.

The summaries listed above will be stratified according to NP positive/negative status and according to prior receipt of any non-study prophylactic COVID-19 vaccine of the subjects. Valid samples for statistical analysis purposes will be those collected: at least 6 and no more than 30 days after Dose 2 for the Week 6 timepoint; at least 174 and no more than 198 days after Dose 2 for the Week 30 timepoint; and at least 356 and no more than 380 days after Dose 2 for the Week 56 timepoint. Baseline is defined as the last measurement prior to the first treatment administration.

The PP population will be used for these immunogenicity analyses.

Phase 3 Segment

Among subjects who are SARS-CoV-2 seronegative at baseline, the primary hypothesis of relative efficacy greater than 30% will be tested with H_0 : $p \ge 0.70/(0.70+k)$ vs. H_1 : p < 0.70/(0.70+k), where p is the true proportion of subjects with disease who receive INO-4800 relative to the total number of subjects with disease, and k is the total amount of follow-up time in the placebo group divided by the total amount of follow-up time in the INO-4800 group.

A p-value for this hypothesis test and corresponding confidence interval will be computed based on the exact binomial method of Clopper-Pearson. Success will be concluded if the one-sided p-value is <0.022 and the corresponding lower bound of the two-sided 95.6% Cl for efficacy exceeds 30% (alpha-level adjusted for interim analyses, see Section 8.5.6), and the point estimate for efficacy exceeds 50%.

For calculating k, an individual subject's follow-up time is either:

- the date of first disease diagnosis date of the start of surveillance period +1 (for subjects who are cases), or
- the date of last follow-up date of the start of surveillance period +1 (for subjects who are non-cases).

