8.5.3 SAFETY ANALYSES

8.5.3.1 Adverse Events

All AEs including injection-site reactions will be summarized among the Safety Population by frequency per treatment arm. These frequencies will be presented overall and separately by dose, and will depict overall, by system organ class and by preferred term, the percentage of subjects affected. Additional frequencies will be presented with respect to maximum severity and to strongest relationship to Study Treatment. Multiple occurrences of the same AE will be counted only once following a worst-case approach with respect to severity and relationship to Study Treatment. All serious AEs will also be summarized as above.

The main summary of safety data will be based on events occurring within 30 days of any dose. For this summary, the frequency of preferred term events will be compared between study arms with risk differences and 95% confidence intervals, using the method of Miettinen and Nurminen. As this analysis will use many event categories, and produce many confidence intervals, caution should be exercised when interpreting these confidence intervals. Separate summaries will be based on events occurring within 7 days of any dose and regardless of when they occurred.

The analyses listed above will be performed according to the Phase of the trial. For the Phase 2 segment, the analyses listed above will also be performed according to prior receipt of any non-study prophylactic COVID-19 vaccine. For the Phase 3 segment, the analyses listed above will also be performed according to SARS-CoV-2 serostatus at baseline.

For AE data, partial start dates will be imputed to the date of treatment to conservatively report the event as treatment-emergent, whenever the portion of the date is consistent

INO-4800	COVID19-311
Inovio Pharmaceuticals, Inc.	Clinical Protocol

with that of the study treatment. Otherwise, it will be imputed to the earliest date consistent with the partial date. A completely missing onset date will be imputed as the day of treatment. Partial stop dates will be assumed to be the latest possible day consistent with the partial date. AE duration will be calculated as (Stop Date – Start Date) + 1.

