8.5.6 INTERIM ANALYSES

For safety issues, the DSMB could recommend stopping enrollment at any time; no formal interim analysis will be performed for this purpose. The two-sided type I error of 0.05 will not be adjusted for possible early stopping due to this aspect.

For the Phase 2 segment, group-level unblinded summaries of the immunogenicity and safety data will be produced once Week 6 visit immunology data and Week 8 visit safety

INO-4800	COVID19-311
Inovio Pharmaceuticals, Inc.	Clinical Protocol

data are complete for all subjects who have not discontinued, while maintaining subjectlevel blinding. Long-term follow-up data will continue to be collected for all subjects who have not discontinued with remaining visits through the final visit. These summaries will allow the Sponsor to have results for the purposes of dose selection for the Phase 3 portion. No subject-level immunogenicity data will be produced, and subject-level immunogenicity data will not be available in the clinical trial database until all other clinical trial data are finalized at the end of the trial. No safety summary will be provided if the total number of subjects who experience the event of interest is greater than 0 and the count of the number of subjects with the event in a given treatment group relative to the total produces a percentage less than 3%, for a given summary. The group-level unblinded production of the summaries will not include anyone directly involved with the trial or any additional unblinded personnel; only the external Contract Research Organization (CRO), ICON, which will already be providing unblinded summaries for the Data Safety Monitoring Board, will be utilized. Thus, the trial will remain blinded to the Sponsor with respect to subject treatment assignment.

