8.6 SAMPLE SIZE/POWER

Phase 3 segment: The trial is case-driven. A total of 149 observed cases among baseline SARS-CoV-2 seronegative subjects will be required to provide 90% power to declare the vaccine efficacious (>30%), assuming a true efficacy of 60% and utilizing the methodology

INO-4800	COVID19-311
Inovio Pharmaceuticals, Inc.	Clinical Protocol

described in Section 8.5.1 and Section 8.5.6. A sample size of 6714 baseline SARS-CoV-2 seronegative subjects will be required to achieve this number of cases assuming an underlying attack rate of 3.7%.

8.7 **RANDOMIZATION AND BLINDING**

Phase 2 Segment

Subjects will be randomized (3 INO-4800 1.0 mg, one injection: 3 INO-4800 2.0 mg, two injections:1 Placebo, one injection: 1 Placebo, two injections).

The study is blinded. It is double-blinded within dose group. Randomization and blinding will avoid bias in the assignment of subjects to treatment, increase the likelihood that known and unknown subject attributes (e.g., demographics and other baseline characteristics) are evenly balanced between treatment groups, and enable valid statistical comparisons between treatment groups. Subject treatment assignments will be unblinded after Phase 2 subjects have reached the Week 30 visit.

Phase 3 Segment

Subjects will be randomized (2 INO-4800:1 Placebo). Randomization will be stratified according to two factors, each with two levels: a) age-group age category (18-50 years vs. ≥51 years) on Day 0, and b) presence or absence on Day 0 of underlying medical conditions that increase risk of severe COVID-19 disease, per US CDC criteria.

The study is double-blinded. Randomization and blinding will avoid bias in the assignment of subjects to treatment, increase the likelihood that known and unknown subject attributes (e.g., demographics and other baseline characteristics) are evenly balanced between treatment groups, and enable valid statistical comparisons between treatment groups.

9.0 **ETHICS**

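### Phase 2 assignments are released at Week 30, but the per-protocol rule, the Week 56 comparison and the whole-trial safety summary were not adapted to an open-label second half

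*Protocol*

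**What the plan says.** Version 2.0USA of the protocol introduces a Week 30 unblinding of Phase 2. Section 5.2.1 says "The Phase 2 segment of the trial will be unblinded following subjects reaching the Week 30 visit", and Section 8.7 says "Subject treatment assignments will be unblinded after Phase 2 subjects have reached the Week 30 visit". The summary of changes at the front of that version puts it at the level of the whole segment: "the Phase 2 segment of the study will be unblinded after all subjects have reached the Week 30 Visit timepoint". The reason given there is that subjects may want to know their assignment when deciding about a non-study COVID-19 vaccine. Section 6.4.7 leaves such vaccination unrestricted in Phase 2, and Section 4.3 asks subjects who take one to stay in the trial. Section 6.1.2 adds: "All subjects will be followed until the Day 393 Visit".

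The analysis text reads as follows.

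- Section 8.4 limits the per-protocol (PP) population to subjects who received all doses and had no protocol violations, with no time limit. It adds: "Subjects excluded from the PP population will be identified and documented prior to unblinding of the trial database".
- Section 8.5.1 compares Phase 2 arms on ELISpot (differences in medians) and neutralizing titre (ratios of geometric mean fold-rises), with 95% CIs, in the PP population, stratified by nucleocapsid status and by prior receipt of a non-study vaccine. Valid samples include those taken "at least 356 and no more than 380 days after Dose 2 for the Week 56 timepoint".
- Section 8.5.3.1 tabulates adverse events by arm, by severity and by strongest relationship to treatment. Beyond the main 30-day summary it says: "Separate summaries will be based on events occurring within 7 days of any dose and regardless of when they occurred".

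**The concern.** The amendment changed the blind without changing the analyses that relied on it. Three outputs are exposed.

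First, the PP rule protects against exclusions made with the arm known. The same PP set serves Week 56, so violations arising after Week 30 fall outside that protection.

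Second, subjects are told their arm partly to help them decide on an outside vaccine. Whether a subject belongs to the vaccinated or unvaccinated stratum at Week 56 can then depend on the arm. Stratifying on that choice conditions on something that happens after randomisation, so a ratio or difference against placebo within a stratum is no longer a randomised contrast, though it would carry the same form of 95% CI as the blinded Week 6 result.

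Third, only SAEs, AESIs and medically attended events (MAAEs) are collected after Day 56. Attendance depends on care-seeking and relatedness on the investigator's judgement, and both can shift once the arm is known. The by-arm table without a time limit adds those reports to the blinded ones without distinguishing them.

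**Working it through.** The plan gives no figure to reproduce here: Section 8.3 describes Phase 2 as estimation without hypotheses. The check is a comparison of texts and a timeline.

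**1. What changed between versions.** Both version 1.0USA and version 2.0USA are in the file.

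| Section | 1.0USA | 2.0USA |
|---|---|---|
| 5.2.1 | blind kept for the whole trial | Phase 2 unblinded at Week 30 |
| 8.4, PP rule | exclusions documented before database unblinding | same wording |
| 8.5.1, Phase 2 analysis | between-arm through Week 56, PP | same wording |
| 8.5.3.1, adverse events | by arm, including any time | same wording |

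No section of 2.0USA sets a PP cut before the Week 30 release or labels later data as open-label.

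**2. Timeline.** Inputs: Dose 2 on Day 28 ± 3, Week 30 on Day 210 ± 5, end of study on Day 393 (Table 3), and the sample windows in Section 8.5.1.

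- Main safety window closes at 28 + 3 + 30 = Day 61. The earliest Week 30 visit is 210 − 5 = Day 205. This summary is wholly blinded.
- Valid Week 56 samples: from 25 + 356 = Day 381 to 31 + 380 = Day 411. If release follows each subject's own Week 30 visit, all of them are taken after release.

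**3. Open-label share.**

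- Release at each subject's Week 30: 393 − 210 = 183 days; 183/393 = 46.6%.
- Within the period when only SAEs, AESIs and MAAEs are collected: 393 − 56 = 337 days; 183/337 = 54.3%.
- Release once all subjects have reached Week 30: a subject enrolled L days before the last one has 183 − L open-label days. The documents do not give the enrolment span, so L is an assumption. L = 0 gives 183 days (47%), L = 90 gives 93 days (93/393 = 24%), and L of 183 or more gives none. The 47% is therefore a maximum.

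**4. PP exclusions.** Two courses are open. If membership is documented before release, it is blind, but a violation after Week 30 cannot be applied although the definition has no time limit. If later violations are applied, they are judged with assignments known. Reading the trial database in Section 8.4 as the final database does not help, because the assignments would already have been released.

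**5. Week 56 strata.** Placebo subjects: 50 + 50 = 100. The documents give no uptake rate. If 30% to 90% of placebo subjects had taken an outside vaccine by Week 56 (assumption), 70 to 10 would remain unvaccinated. This shows sensitivity only. Outside vaccination was already unrestricted in 1.0USA, so the loss cannot all be attributed to unblinding.

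**The case against.** The strongest reply is that little of consequence depends on the exposed outputs. Phase 2 has no hypotheses, dose selection used Week 6 immunogenicity and Week 8 safety, and Phase 3 data are independent. The immunogenicity endpoints are laboratory assays, and Section 8.5.6 keeps subject-level results out of the database until all other data are final, so exclusions cannot be chosen on results. Both doses are complete by about Day 31, sample validity is an objective day window, and outside vaccination is not restricted and so not evidently a violation. All of this stands and limits the size of the problem. It does not make later exclusions blind to arm, nor does it restore randomisation within strata formed by an informed choice.

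Some stronger inferences are tempting and should not be drawn.

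- A reader might infer that open-label safety differences carry confidence intervals. Section 8.5.3.1 attaches the Miettinen–Nurminen risk differences and CIs only to the 30-day summary; the any-time output is by-arm frequencies.
- A reader might take "Thus, the trial will remain blinded to the Sponsor with respect to subject treatment assignment" in Section 8.5.6 as contradicting the unblinding. It closes the account of the Week 6 and Week 8 group-level summaries and concerns only that exercise.
- A reader might conclude that PP exclusions can only be made unblinded. Membership can be documented before release; the plan simply does not say so.
- A reader might assume that no event in a known placebo recipient would be called related. Section 7.10.4 assesses drug and device, and placebo recipients also receive electroporation. Relatedness is open to influence, but its direction and size are not established.

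**Conclusion.** The point holds in a limited form. Following the 2.0USA text would use one PP set across blinded and open-label periods, report a Week 56 comparison with placebo that known assignment can shape through vaccine choice, dropout and exclusions, and pool blinded with open-label reports in the any-time safety summary. The exposed part is at most 183 of 393 days (47%) per subject and one of three post-baseline immunogenicity timepoints. The size of any bias cannot be derived from the documents.

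The 30-day safety comparison, the Week 6 and Week 8 dose selection and all of Phase 3 are unaffected. The change is worth making, but it does not threaten the trial's main conclusions.

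The conclusion rests on the nominal visit schedule and on version 2.0USA. The file also shows a page marked version 7.0 whose analysis sections are not included, so whether later wording closes the gap is unknown. Section 8.1 says the formal analysis plan is Section 8 itself, so the stated wording is what would be followed.

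**What to change.** 1. Section 8.4: require Phase 2 PP membership to be documented before the Week 30 release, and allow only objective rules fixed by that date to be applied to later data.
2. Section 8.5.3.1: end the whole-trial by-arm Phase 2 summary, including relatedness, at the unblinding date. Show later SAEs, AESIs and MAAEs separately as open-label.
3. Section 8.5.1: report Week 56 primarily as within-arm persistence. Label any comparison with placebo at that timepoint as open-label and non-randomised.
4. Sections 5.2.1 and 8.7: state whether release is subject by subject or, as the summary of changes describes it, after all subjects have reached Week 30. The cut-off date in item 2 depends on this.

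The cost is some wording, one extra data cut in the tables and a less prominent Week 56 comparison with placebo. No new visits or data are needed.
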